Doc id

**Revision Author** 

PPD

Date

07 JUL 2020

**MA-42004** 

Doc id

Comments

Month 6 visits are now month 7. Any patient

Incorporated changes from CIP V4 of protocol:

with a month 6 visit will use that as a surrogate for their month 7 visit for secondary endpoint purposes

### **Revision History**

Version

2.0

3.0

4.0

5.0

Galderma Research and Development, LLC	
Confidential and Proprietary	

		2. Many endpoints at month 9 visits are now at month 12 – including primary endpoint
		3. PP population is now based on month 12 visit and primary endpoint
		4. Changed BOCF to Multiple Imputation
		5. Updated schedule of events
		6. Device deficiencies will be summarized
15 JAN 2021	PPD	Added information on multiple imputation for the primary analysis (section 2.4.3 Multiple Imputation )
23 MAR 2021	PPD	1. Amended the number of FST V-VI subjects to be at least 14 in alignment with the protocol amendment v5
		2. Remove an erroneous mention to an unused endpoint, the WAS
		3. Define how nodules, papules, and granuloma are defined from AEs
		
 
Clarify that AE's by injection technique include combinations of injection techniques
 

30 JUL 2021	PPD	1. Moved "other effectiveness endpoints" to new section 2.4.6. Added information here on summarizing subjects with incorrect gain for dermal thickness.
		2. Elaborated on how Snellen acuity will be summarized via Snellen decimal categories.

1.

#### 1 **Study Information**

#### Background 1.1

This statistical analysis plan (SAP) describes the analysis variables and statistical procedures that will be used to analyze and report the results from Protocol 43USSA1812 (v3.0), dated 20 September 2019.

The SAP was written in accordance with the recommendations outlined in the International Conference on Harmonisation (ICH) E9 Guideline entitled "Guidance for Industry: Statistical Principles for Clinical Trials" and the ICH-E3 Guideline entitled "Guidance for Industry: Structure and Content of Clinical Study Reports".

#### 1.1.1 Study Design

This is a prospective, randomized, evaluator-blinded, no-treatment controlled study. Approximately 150 subjects will be randomized (2:1) to either treatment with Sculptra Aesthetic (Treatment Group) or no treatment (Control Group), 100 subjects to treatment with Sculptra Aesthetic and 50 subjects to no treatment. At least 15 subjects will be Fitzpatrick skin type (FST) IV, and at least 14 will be FST V-VI.

Effectiveness and safety data will be collected for up to 12 months following the initial treatment.

All subjects will be offered to participate in an open extension study beginning after successful completion of this study. Subjects in the no-treatment control group will be offered treatment with Sculptra Aesthetic in the extension study. Subjects in the treatment group will continue to be followed for additional data collection as described in the extension study protocol.

#### 1.1.2 Number of Subjects

The study is planned to enroll approximately 150 subjects at approximately 13 centers in the United States.

#### **Study Objectives** 1.2

For the study to be deemed successful, the following criteria need to be met:

- The primary effectiveness endpoint, CC ٠ , should be statistically significantly greater in the Treatment Group when compared to the Control Group.
- Acceptable safety profile in the treatment group. •

#### 1.2.1 **Effectiveness Objectives**

To evaluate the effectiveness of Sculptra Aesthetic versus a no-treatment control in the correction of cheek wrinkles.

#### 1.2.2 Safety Objectives

To evaluate the safety of Sculptra Aesthetic in the correction of cheek wrinkles.

Galderma Research and Development, LLC Confidential and Proprietary

Statistical Analysis Plan Version 5.0, 30 Jul 2021

#### 1.3 Effectiveness Assessments

For all assessments, baseline will be defined as the observation that is closest to but prior to study treatment on Day 1 for treated patients. For non-treated patients, baseline will be defined as the observation that is closest to but prior to randomization. Likewise, change from baseline will be calculated as the value at a given time point minus the baseline value.

### 1.3.1

The severity of cheek wrinkles will be assessed live by the Blinded Evaluator and the Treating Investigator using the validated 5-graded during the study. The scale is a validated photograph-based outcome instrument. A photo guide of the scale is provided in the protocol. The subject is to have a relaxed face during the assessment.

will be assessed live by the Blinded Evaluator at screening/baseline and at The months 7, 9, and 12 after baseline. The will be assessed live by the Treating Investigator at screening/baseline and at each treatment visit. However, the Treating Investigator will not be included in any statistical analyses since these assessments are only made to decide whether further treatment is needed. See Table 1 for categorical scales used.

## 1.3.2

The severity of cheek wrinkles will be assessed live by the Blinded Evaluator using the validated 5during the study. The scale is a validated photographgraded based outcome instrument. A photo guide of the scale is provided in the protocol. The subject is to have a closed maximum smile during the assessment.

The will be assessed live by the Blinded Evaluator at screening/baseline and at months 7, 9, and 12. The will be assessed live by the Treating Investigator at screening/baseline and at each treatment visit. However, the Treating Investigator will not be included in any statistical analyses since these assessments are only made to decide whether further treatment is needed. See Table 1 for categorical scales used.

#### Global Aesthetic Improvement Scale (GAIS) 1.3.3

The aesthetic improvement of cheek wrinkles will be assessed by the Treating Investigator and the subject, independently of each other. Baseline photographs may be used as a comparison for the GAIS evaluation.

Galderma Research and Development, LLC Confidential and Proprietary

The Treating Investigator and the subject will, independently of each other, respond to the question: "How would you describe the aesthetic improvement today compared to the photograph taken before treatment?"

GAIS will be assessed by the Treating investigator and subject at months 7, 9, and 12. The following categorical scales will be used (Table 2).

## 1.3.4 Subject Satisfaction Questionnaire

Subject satisfaction with treatment result will be assessed by using a subject satisfaction questionnaire (Section 7.4 of the protocol) at all visits following the baseline visit for the Treatment Group.

### 1.3.5 FACE-Q "Satisfaction with Cheeks"

The FACE-Q is a patient-reported outcome instrument to evaluate the experience and outcomes of aesthetic facial procedures from the subject's perspective at all visits following the Baseline visit for the Treatment Group and at months 7, 9, and 12 for the Control Group

#### 1.3.6 Subject Diary

A subject diary will be dispensed to all subjects in the Treatment Group for daily completion for 28 days beginning on injection day for each treatment with direct questioning for pain, tenderness, redness, bruising, swelling, itching, lumps/bumps and "other". Subjects will be specifically asked to record any of the following symptoms in the other section: changes in vision (i.e. loss of vision, blurriness, double vision, pain in or around your eye, blindness, blind spots, problems moving your eyes), skin changing color around the eyelids, crusty or scabby skin around the eyelids, pain, headache, fever, dizziness, confusion, weakness or numbness in the arms or legs, changes to consciousness or alertness, difficulty speaking/speech impairment and face droop.

#### Return to Social Engagement

Subjects will be asked to complete the following questions in the subject diary: Did you feel comfortable returning to social engagement today? If yes, what was the earliest time you felt comfortable to return to social engagement?

Returning to social engagement is defined as making public/social appearances, including but not limited to returning to work at a business office or other public work place; having dinner in a public restaurant; attending a social event/gathering such as dinner party, etc. Subjects will record the time they felt comfortable (with or without covering make-up) resuming social interactions, not necessarily the time for their first social interaction.

#### 1.4 Effectiveness Endpoints

#### 1.4.1 Primary Effectiveness Endpoint

The primary measure of effectiveness is the responder rate based on the

, as assessed live by the Blinded Evaluator at month 12.

A responder is defined as a with at least 1 grade improvement from baseline on both cheeks concurrently.

### 1.4.2 Secondary Effectiveness Endpoints

Secondary effectiveness endpoints include:

- 1. Responder rate based on the **second second**, as assessed live by the Blinded Evaluator at month 7 and 9. A responder is defined as a subject with at least 1 grade improvement in both cheeks concurrently from baseline.
- 2. Responder rate based on the **second second**, as assessed live by the Blinded Evaluator at month 7, 9 and 12. A responder is defined as a subject with at least 1 grade improvement in both cheeks concurrently from baseline.
- 3. Improvement rate based on the Independent Photographic Reviewer's assessment using random pairings of baseline and month 12 photographs.

Treatment group: An improved subject is defined as a subject for whom the Independent Photographic Reviewer correctly identified the month 12 photograph in the pair of pre- and post-treatment photographs at rest.

Control group: An improved subject is defined as a subject for whom the Independent Photographic Reviewer identified any of the photographs in the pair as post-treatment at rest.

- 4. Percentage of subjects having at least "Improved" according to the GAIS on both sides of the face combined, as assessed live by the subject and the Treating Investigator separately, at all visits following the Baseline visit for the Treatment Group and at month 7, 9 and 12 for the Control Group.
- 5. Percentage of subjects responding in each response category for each question in the subject satisfaction questionnaire at all visits following the Baseline visit for the Treatment Group.
- 6. Change from baseline in subject satisfaction using the Satisfaction with Cheeks FACE-Q questionnaire with Outcome Rasch transformed total scores as well as percentage of subjects in each response category for each of the individual questions at all visits following the

Galderma Research and Development, LLC Confidential and Proprietary

Effective date: 2021-08-30 14:55

Doc id

Baseline visit for the Treatment Group and at month 7, 9 and 12 for the Control Group.

7. Time to feeling comfortable returning to social engagements after treatment using subject diaries for 28 days after each treatment.

### 1.5 Safety Assessments

The methods for collecting safety data are described in Section 8 of the Clinical Study Protocol.

## 1.6 Safety Endpoints

Safety endpoints include:

- 1. Incidence, intensity, time to onset and duration of adverse events collected throughout the study period.
- 2. Incidence, intensity and number of days of pre-defined expected post-treatment events collected using subject diaries for 28 days from each treatment.
- 3. Safety assessment by a qualified staff member at all visits according to predefined methods at baseline and at all follow-up visits for the Treatment Group and the Control Group:
  - Cheek firmness, symmetry and function
  - Device palpability (baseline assessment excluded)
  - Mass formation
  - Cheek sensation
  - Visual Function Assessments

## 2 Statistical Methods

## .1 General Methods

Any change made to the finalized SAP before database lock will result in a SAP amendment. Otherwise, the change will be documented in the Clinical Study Report (CSR).

Some of the analyses detailed here may be more explicit or in some aspects different from those stated in the protocol. In case of differences, this SAP supersedes the statistical sections in the protocol.

## 2.1.1 Programming Conventions

Statistical Solutions will have responsibility for performing analyses. All computations for statistical analyses will be performed using SAS® software, Version 9.4 or later. All SAS programs used in the production of statistical summary outputs will be validated with independent programming prior to finalization. In addition, all program outputs will be independently reviewed. The validation process will be used to confirm that all data manipulations and calculations were accurately done. Once validation is complete, a senior statistical reviewer will perform a final review of the documents to ensure the accuracy and consistency with this plan and consistency within tables. Upon completion of validation and quality review procedures, all documentation will be collected and filed by the project statistician or designee.

The electronic case report form (eCRF) data for all subjects will be provided in Standard Data Tabulation Model (SDTM) datasets. Analysis Data Model (ADaM) datasets will be developed from the SDTM datasets for use in table and figure production.

## 2.1.2 Reporting Conventions

The formats for the tables, listings, and figures described in this SAP will be provided in a companion document. Changes to the formats of these reports that are decided after the finalization of the SAP will not require an amendment. In addition, any additional supportive or **CC** analyses requested after SAP approval will not require amendment of the SAP. These additional analyses will be described in the CSR.

All study data from the eCRFs as well as derived variables will be provided in subject data listings. An indication of specific listings for each data type will not be indicated in the text of subsequent SAP sections. Data listings supplied as part of the CSR will be sorted by study center number concatenated with subject number, assessment dates, and/or time point.

The following conventions will be applied to all data presentations and analyses:

- Quantitative variables will generally be summarized by the number of subjects, mean, standard deviation (SD), median, minimum (min), and maximum (max). Unless otherwise specified, the minimum and maximum values will be displayed to the same number of decimal places as the raw data, the mean and median will be presented to one extra decimal place compared to the raw data, and the standard deviation will be displayed to two extra decimal places compared to the raw data
- Categorical variables will be summarized by the number and percentage of subjects (and number of events where appropriate) within each category. Unless otherwise specified, the percentage will be presented in parentheses to one decimal place. Frequency and percentage values of 0 will be presented as '0' rather than '0 (0)'.
- All summary tables will include the analysis population sample size (i.e. number of subjects).
- Date variables will be formatted as DDMMMYYYY for presentation.

Statistical Analysis Plan Version 5.0, 30 Jul 2021

Doc id

## 2.1.3 Data Transformations

The Rasch transformation scoring of the FACE-Q will be reported (Section 4).

## 2.2 Analysis Populations

The statistical analyses will be performed based on the following subject populations.

## 2.2.1 Intent-to-Treat (ITT) Effectiveness Population

Includes all subjects who were randomized based on the as randomized principle (i.e. according to the treatment they were randomized to).

## 2.2.2 Per-Protocol (PP) Effectiveness Population

Includes all subjects in ITT with a completed 12 month after baseline assessment of the Blinded Evaluator **evaluator**, and without any deviations considered to have substantial impact on the primary effectiveness outcome.

## 2.2.3 Safety Population

Includes all subjects who were treated with Sculptra Aesthetic or randomized to no treatment control group. Subjects are analyzed based on the as treated principle (i.e. according to the treatment actually received).

## 2.3 Study Subjects

Demographic endpoints and subject characteristics will be summarized using descriptive statistics by treatment group and overall based on the ITT population using the Observed Cases (OC). There are no planned inferential statistical analyses of demographic endpoints or subject characteristics.

## 2.3.1 Subject Disposition

The number of subjects screened will be shown in total and by study center.

The number of subjects in each study population (i.e. ITT, PP, and Safety) will be summarized by study center and in total.

The disposition of subjects will be summarized, including numbers of subjects who were:

- Randomized,
- Completed,
- Withdrawn (including primary reason for withdrawal).

These numbers will be summarized by study center. The number of subjects expected, completed, missed, and withdrawn will be summarized by scheduled visit.

- Expected = all subjects minus withdrawn subjects.
- Completed = subjects that showed up at that visit.
- Missed = expected subjects minus completed subjects.
- Withdrawn = all subjects who have withdrawn up to that visit.

Galderma Research and Development, LLC Confidential and Proprietary

Version:

All withdrawn subjects will be listed individually, by subject number, date and reason for withdrawal, and last visit performed.

#### 2.3.2 Protocol Deviations

Subjects with any protocol deviations will be summarized by treatment group, overall, by site, and by type.

Depending on the seriousness of the deviation, a subject might be excluded from the PP population, which shall be documented prior to database lock. Reasons for exclusion from the PP population will be summarized.

#### 2.3.3 Demographic Characteristics

Age, weight, and body mass index (BMI) will be summarized as continuous variables. Weight and BMI will additionally be summarized at each visit along with change from baseline.

Gender, age category (≥55 vs <55), race, ethnicity, Fitzpatrick skin type and baseline (Blinded Evaluator and Treating Investigators) will be summarized as categorical variables.

vuriuores.

### 2.3.4 Medical History, Medications, and Procedures

Prior and concomitant medications will be coded using the World Health Organization Drug Dictionary (WHODD). Medical history, and prior and concomitant procedures/non-pharmacological treatments will be coded according to MedDRA.

Prior medications/procedures are the medications/procedures with stop dates prior to study treatment. Medications/procedures after the study treatment will be considered concomitant.

Subjects reporting medical history, cosmetic treatments/procedures, and prior and concomitant procedures/non-pharmacological treatments will be summarized by system organ class (SOC) and Preferred Term (PT).

Subjects reporting prior and concomitant medications will be summarized separately, by WHODD Anatomical Therapeutic Chemical (ATC) Class Level 3 (if Level 3 is not available, the highest class available will be used) and WHODD generic name.

### 2.4 Effectiveness Analysis

#### 2.4.1 Datasets Analyzed

ITT is the primary population for all effectiveness analyses. The primary effectiveness analysis will be repeated using the PP analysis set if there is at least a 10% difference in the number of subjects between the PP and ITT sets. Safety analysis is performed based on the safety population set.

### 2.4.2 Handling of Missing Data

Number of missing values will be summarized and reported as appropriate.

For ITT analysis of the Blinded Evaluator responder rate at month 12 (primary endpoint), missing values will be imputed via multiple imputation. Only patients with a baseline

Doc id

score will be included in this analysis. Impact of missing data on the primary endpoint will be evaluated by performing sensitivity analysis based on the observed cases in the ITT set.

A small number of patients may have a month 6 visit rather than month 7. These patients' month 6 visit will be used as a conservative surrogate for their month 7 visit results, and pooled with the month 7 visit data.

All other effectiveness endpoints will be evaluated based on the observed cases in ITT.

Descriptive statistics of all safety data will be performed on observed cases.

## 2.4.3 Multiple Imputation

The multiple imputation (primary analysis only) will assume Missing Completely at Random (MCAR). Regardless of the actual pattern of missing data, the Full Conditionals (FCS) option of the MI procedure from the SAS® system will be used to generate ten sets of data with missing values imputed from observed data. The observed data used to impute missing Month 12 values for each side of the face are as follows: treatment, side of face, and all previous scores (including the following visits: screening, baseline, and months 7, 9, and 12). The FCS option with no arguments will be employed to model the missing left and right scores separately, which is equivalent to a regression model which uses all variables as covariates. To achieve such a model.

The imputed datasets will be analyzed using the methodology described for the primary analysis. In terms of the continuous mapping of the **multiple** imputation, a responder will be defined as a subject with at least an improvement of 1 in both cheeks concurrently from baseline. Responder rates, difference in responder rates, and the associated confidence intervals will be combined by the MIANALYZE procedure of the SAS® system. The mean value of the Fisher's Exact Test p-values across imputations will be reported. The seed number to be used will be the last four digits of the protocol number (1812).

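### SAP 2.4.3 applies a raw cut-off of 1.0 to continuous imputed scores, so both month-12 responder rates read low even under the SAP's own MCAR assumption

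*SAP*

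**What the plan says.** The primary scale has five grades (SAP 1.3.1: "using the validated 5-graded during the study"; the scale name is blacked out). SAP 1.4.1 defines a responder by "at least 1 grade improvement from baseline on both cheeks concurrently".

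SAP 2.4.3 limits multiple imputation to the primary analysis and assumes that data are missing completely at random (MCAR). It generates ten imputed data sets. On the model it says: "The FCS option with no arguments will be employed to model the missing left and right scores separately", and calls this "equivalent to a regression model which uses all variables as covariates". It acknowledges that the imputed values are continuous and then sets the rule: "a responder will be defined as a subject with at least an improvement of 1 in both cheeks concurrently from baseline". The visible text contains no rounding step, ordinal model or predictive mean matching.

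Everything else on effectiveness uses observed data. SAP 2.4.2 says: "All other effectiveness endpoints will be evaluated based on the observed cases in ITT". That covers the secondary responder rates "as assessed live by the Blinded Evaluator at month 7 and 9" (SAP 1.4.2). An observed-case analysis of the primary endpoint is planned as a sensitivity analysis.

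**The concern.** The same nominal cut-off does different work on the two kinds of data. For whole-grade scores, a cut-off of 1 accepts every one-grade improver. For a continuous draw it rejects any value from 0.50 to 0.99, although the nearest grade is a one-grade improvement. Because both cheeks must pass, the loss compounds. Imputed subjects are held to a stricter standard than observed ones, so the month-12 rates are biased downward under the assumption the SAP itself makes.

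Three things are at stake:

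- This analysis decides success (SAP 1.2) and supplies the reported month-12 responder rates.
- Months 7 and 9 use observed cases while month 12 uses imputation. A constant true rate would appear to fall from month 9 to month 12 purely because of the scoring rule.
- If control subjects dropped out more often than treated subjects, the rule would create a small false difference in favour of the product. The documents do not predict this. The offer of treatment in the extension study (SAP 1.1.1) is a reason for controls to stay.

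**Working it through.** **Inputs from the documents.** 70% versus 35% response, 84 and 42 evaluable, 15% dropout, about 150 randomized 2:1 (SAP 2.7); Fisher's exact test, two-sided p < 0.05 (SAP 2.4.4); mean Fisher p-value over ten imputations (SAP 2.4.3); baseline Moderate or Severe on each side (protocol 5.2).

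**The plan's own figure.** For 84 versus 42, power is 97.0% by the pooled chi-square formula and 95.7% by exact enumeration of Fisher's test, against a stated figure of about 90%. The total reproduces: 126 / 0.85 = 148.2, so 149. The stated power is conservative, and this does not affect the point here.

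**Hand check of the mechanism, one cheek.** Suppose improvement is 0 or 1 grade with probability p of 1. A normal draw with the same mean p and SD √(p(1−p)) passes a cut-off c with probability 1 − Φ((c − p)/SD).

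- p = 0.70: SD = √0.21 = 0.458. At c = 1.0, 1 − Φ(0.655) = 26%. At c = 0.5, 1 − Φ(−0.436) = 67%.
- p = 0.35: SD = √0.2275 = 0.477. At c = 1.0, 1 − Φ(1.363) = 9%. At c = 0.5, 1 − Φ(0.314) = 38%.

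Baseline is a whole grade, so rounding to the nearest grade is the same as c = 0.5.

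**Simulation of the planned case.** 100 versus 50 subjects, ten imputations, baseline grade 2 or 3 on an assumed 0–4 coding. Whole-grade scores at months 7, 9 and 12 come from a latent normal change with means set to give 70% and 35% both-cheek response at each visit. My assumptions, since the documents give none: latent SD 0.5, 0.7 or 0.9; between-cheek correlation 0.5, 0.7 or 0.85; between-visit correlation 0.6; MCAR dropout starting at month 7, 9 or 12 with equal chance. The regression draws use treatment and the scores of both cheeks. Ranges are over the nine settings.

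| 15% dropout in each arm | Treated | Control |
|---|---|---|
| Subjects imputed | 15 | 7.5 |
| True response | 70% | 35% |
| Response among imputed, SAP rule | 27–44% | 8–16% |
| Imputed responders counted (expected) | 4.1–6.6 (10.5) | 0.6–1.2 (2.6) |
| Arm rate, SAP rule | 63.7–66.2% | 30.8–32.0% |
| Shortfall against simulated complete data, points | 3.9–6.4 | 2.8–4.0 |
| Imputed / arm rate after rounding | 62–67% / 69.0–69.6% | 31–34% / 34.4–34.7% |
| Imputed / arm rate, predictive mean matching | 69–70% / 70.0–70.1% | 35–36% / 34.7–35.0% |

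Check with arm rate = 0.85p + 0.15q, where q is response among the imputed. Treated: 59.5 + 0.15 × 27 = 63.6 and 59.5 + 0.15 × 44 = 66.1. Control: 29.75 + 0.15 × 8 = 30.95 and 29.75 + 0.15 × 16 = 32.15. These agree with the table to about 0.2 points.

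The difference between arms shrinks by 1.0–2.4 points. Power is 96–97%, against 98% with complete data. The artificial fall from month 9 to month 12 is 3.9–6.3 points (treated) and 2.9–4.2 (control).

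**Sensitivity.**

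- Dropout 10%: arms 2.7–4.4 and 1.9–2.7 points low. Dropout 5%: 1.3–2.2 and 1.0–1.4.
- If 89–97% of responders improve two or more grades in at least one cheek: 0.7–1.9 and 0.4–1.4 points low.
- If modelling the cheeks separately means leaving the other cheek out: imputed response 19–38% and 4–11%, arms 4.8–7.7 and 3.7–4.8 points low.
- A second simulation with different variance structures and both readings of the model (16 scenarios) gave imputed response of 22–50% and 4–23%. Both arms were low in every scenario. With true control rates of 5–30%, the control arm was still about 0.5–2.5 points low.

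**Unequal dropout, 35% true response in both arms, 22.5 of 150 missing** (100 × 0.15 + 50 × 0.15 = 100 × 0.13 + 50 × 0.19 = 100 × 0.10 + 50 × 0.25).

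| Dropout treated/control | False difference, points | Rejection rate |
|---|---|---|
| 15% / 15% | none | 3.2–4.0% |
| 13% / 19% | 1.1–1.6 | 3.4–4.0% |
| 10% / 25% | 2.8–3.9 | 4.1–5.8% |

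At 10%/25%, 3.6–5.3% of trials reject in favour of the product, against 2.2–2.4% with complete data. Rounding leaves 0.2–0.5 points of false difference, and predictive mean matching 0.2–0.4.

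**The case against.** The case for leaving the rule alone has real substance.

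- **The success decision is almost untouched.** In the planned case the error runs against the product, power stays far above 90%, and false rejection under equal dropout is below 5%. This stands, and it limits how serious the point is.
- **The protocol's method was harsher.** Protocol 10.6 carries the baseline forward, so every missing subject fails: 0.85 × 70 = 59.5% and 0.85 × 35 = 29.75%. The SAP rule is milder and errs in the same direction. But SAP 2.1 says the SAP supersedes the protocol's statistical sections, and the SAP replaced lack of effect with MCAR. Under MCAR the rule gives the wrong rate.
- **The cut-off was chosen knowingly.** The SAP does recognise that the values are continuous. That does not make the rule equivalent to the one for observed grades.
- **The text is damaged here.** A sentence just before the responder paragraph breaks off, and a word is missing from the clause that introduces the rule. A rounding step could have been lost, but the responder sentence itself is complete.
- **The size is uncertain.** It depends on an unseen score distribution, and 15% is a sample-size allowance. In an extreme one-cheek case with improvement of 0 or 2 grades, the cut-off of 1 gives 67% for a true 70% and 38% for a true 35%, so the control direction can reverse.
- **Unaffected analyses sit alongside.** The observed-case analysis escapes the problem. So does the per-protocol repeat, which 15% dropout would trigger because it exceeds the 10% threshold in SAP 2.4.1. Neither decides success, and both would disagree with the primary result for an artificial reason.

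**Conclusion.** The concern holds. As written, the rule is internally inconsistent: under its own MCAR assumption it understates both month-12 responder rates, by 3.9–6.4 points (treated) and 2.8–4.0 points (control) at the planned rates and 15% dropout. The shortfall is roughly proportional to the dropout fraction.

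The direction is robust over the plausible settings examined. The size rests on the assumed latent SD and correlations, and it drops to 0.7–1.9 and 0.4–1.4 points if most responders improve by two or more grades. The effect on power is negligible. The risk of a false difference favouring the product arises only if control dropout clearly exceeds treated dropout, which nothing in the documents suggests. It should be corrected because it biases the headline rates for no benefit. The conclusion would change only if a rounding step exists in lost text or in the programs.

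**What to change.** Replace the responder sentence in SAP 2.4.3 with wording such as: *Missing month-12 scores will be imputed on the 5-grade scale by FCS predictive mean matching (or ordinal logistic regression), with treatment and the scores of both cheeks at all visits in the model. A responder has an improvement of at least 1 whole grade in both cheeks.*

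The minimum change is: *Imputed scores will be rounded to the nearest grade before the responder rule is applied.*

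In either case, state that both cheeks are in the model. If each cheek is imputed without the other, rounding alone leaves imputed response at 55–64% and 22–28%. If the programs already round, one sentence saying so is enough.

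The cost is one or two SAP sentences and one option in the imputation code, with no new data. There are limits. Predictive mean matching draws on a limited number of observed donors. Rounding leaves up to 1.0 (treated) and 0.6 (control) points of bias in the planned case. If most responders improve by two or more grades, both remedies read slightly high, by 0.1–0.4 points (treated) and 0.6–0.9 (control).
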